3.5 If applicable, please select the Designated Department Approval(s)	
[name], [name] Department Chair Add the name of the individual authorized to approve and sign off on this protocol from your Department (e.g. the Department Chair or Dean).	
4.0	

Initial Screening Questions

Updated June 2017

4.1 * PROJECT SUMMARY: (REQUIRED) Give a brief overview of this project (250 words or less). Tell us what this study is about, who is being studied, and what it aims to achieve. If you have an NIH Abstract, paste it here: Click on the orange question mark to the right for more detailed instructions.

BACKGROUND:

There is a need for cost-effective infertility treatments. For women requiring in-vitro fertilization (IVF), intra-vaginal culture (IVC) of embryos can be used as a lower-cost alternative, using the INVOcell® device.

HYPOTHESIS:

In women with infertility requiring IVF, we will see similar clinical pregnancy rates (CPR) with minimal gonadotropin or oral medication stimulation using the INVOcell device compared with conventional IVF.

PRIMARY AIM:

To determine outcomes of IVC with INVOcell device versus conventional IVF while using oral stimulation or minimal gonadotropins stimulation protocols:

a. Implantation rate	
SECONDARY AIMS: To determine the effect of IVC with INVOcell device versus conventional IVF while using oral stimulation or minimal gonadotropins stimulation protocols on:	
a. Fertilization rateb. Embryo qualityc. Clinical pregnancy rated. Live birth rate	
DESIGN Non-blinded prospective randomized controlled trial pilot study	
4.2 * HUD DEVICE: (REQUIRED) Does this application involve a Humanitarian Use Device (HUD):
NoYes, and it includes a research componentYes, and it involves clinical care ONLY	
4.3 * TYPE OF RESEARCH: (Click the Help link for definitions and guidance): (REQUIRED)	
 Biomedical research Social, behavioral, educational, and/or public policy research Hybrid - includes aspects of BOTH types of research (check this option if your research is mainly social/behavioral but also involves specimen collection or blood draws to look at biological measures) 	
4.4 * SUBJECT CONTACT: (REQUIRED) Does this study involve ANY contact or interactions participants:	with
Yes (including phone, email or web contact)No (limited to medical records review, biological specimen analysis, and/or data analysis)	
4.5 * RADIATION EXPOSURE: Does your protocol involve any radiation exposure to patient EITHER from standard care OR for research purposes (e.g., x-rays, CT-scans, DEXA, CT radiation therapy, or nuclear medicine including PET, MUGA or bone scans): (REQUIRE	-guided biopsy,
O Yes ⊙ No	
4.6 * RISK LEVEL: (REQUIRED) What is your estimation of the risk level, including all scree procedures and study activities (Help Text updated 9/13):	ening
Minimal riskGreater than minimal risk	
4.7 * REVIEW LEVEL: (REQUIRED) Requested review level (Click on the orange question maright for definitions and guidance):	ark to the
© Full Committee © Expedited © Exempt	
4.11 * CLINICAL TRIAL: (REQUIRED) Is this a clinical trial? According to The World Heal (WHO) and the International Committee of Medical Journal Editors (ICMJE) a clinical	

• Any research study that prospectively assigns human participants or groups of humans to one or more health-related interventions to evaluate the effects on health outcomes.

ICMJE requires registration of a clinical trial in a public database (such as ClinicalTrials.gov) prior to enrollment, for eventual publication of results in member biomedical journals. Guidance: Public Law 110-85 requires that all investigators who perform an *applicable clinical trial* must ensure that the trial is registered on a government web site called ClinicalTrials.gov. The FDA requires registration for "applicable clinical trials," defined as follows:

- For any trials of drugs and biologics: controlled clinical investigations, other than Phase 1 investigations, of a product subject to FDA regulation.
- For trials of biomedical devices: controlled trials with health outcomes of devices subject to FDA regulation, other than small feasibility studies, and pediatric post-market surveillance.

For additional information on the ClinicalTrials.gov registration process at UCSF and the definition of a clinical trial for purposes of registration, visit the ClinicalTrials.gov section of the UCSF Clinical Research Resource HUB.

⊙ Yes ○ No	
Clinical Trial Registration "NCT" number for this trial:	
NCT02802176	
If you don't yet have the NCT#, type 'Pending.'	
4.12 * CLINICAL TRIAL PHASE (REQUIRED) Check the applicable phase(s) (Help Text update)	nted 9/13):
□ Phase I □ Phase II □ Phase III □ Phase IV	
4.13 * INVESTIGATOR-INITIATED: (REQUIRED) Is this an investigator-initiated study:	
⊙ Yes ○ No	
4.14 SCIENTIFIC REVIEW: If this study has undergone scientific or scholarly review, pleas which entity performed the review (check all that apply):	e indicate
 □ Cancer Center Protocol Review Committee (PRC) (Full approval is required prior to final CHR approval for cancer-related protocols.) □ CTSI Clinical Research Services (CRS) Advisory Committee □ CTSI Consultation Services □ Departmental scientific review □ Other: 	
4.15 * STEM CELLS: (REQUIRED) Does this study involve human stem cells (including iPS of stem cells), gametes or embryos:	cells and adult
 No Yes, and requires CHR and GESCR review Yes, and requires GESCR review, but NOT CHR review 	
4.16 * FINANCIAL INTERESTS: (REQUIRED) Do you or any other responsible personnel registered domestic partner and/or dependent children thereof) have financial intere	

	this	stu	dy:							
0	Yes (• N	0							
5.0	Fu	ıno	ding							
5.1				EQUIRED) Is this st	udv current	lv support	ted in wh	ole or in pa	art by Federal	
			•	ontract, OR has it red	•			•	,	
0	Yes (• N	0							
5.2	* Do (REQ			this project linked	in any way t	o the Dep	artment	of Defense	(DoD):	
0	Yes (• N	0							
5.3			-	sponsors and provid only the Prime Spon		g details.	If fundir	ng comes fro	om a	
E>	cter	na	l Sponsor	s:						
								UCSF RAS		
_	iew	Spo	nsor Name	Sponsor Type	Awardee	Contract	"	System Award		
De	etails				Institution:	Type:	Number	Number ("A" + 6		
No	Spon	sor h	as been added to	this IRB Study				digits)		
T.C	ح ما ا	c	- d: :		LICCE -		طاء مال	les acce		
			•	ming through you can seaı		-				
				nt (this does N		-				
sp	ons	or	by name a	bove AND ent	ering th	e A or	P num	nber):		
	Proje	ct S	tatus Propos	al Number P	roject Title			ncipal vestigator		
No	Proje	cts a	re Linked to this	IRB Study						
Ot	thei	· F	undina So	urces and U	nfunde	d Rese	earch	_		
Gi	ft,	Pro		Internal Fur						
	ply		aift (anasif :	co holow)						
	Funde	d by		program (specify sour						
				ng (specify source belo partmental funding)	w)					
	Unfund	ded s	tudent project							

^{6.0} Sites, Programs, Resources, and External IRB Review	W
6.1 UCSF AND AFFILIATED SITES (check all that apply):	

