7.1	This new consolidated section requests information about: • Hypothesis • Aims • Study Design • Background and Significance • Preliminary Studies • Procedures • Statistical Methods • References Later sections include: • Drugs and Devices • Sample Size, Eligibility, and Subjects • Recruitment and Consent • Risks and Benefits • Data and Safety Monitoring Plan • Confidentiality, Privacy and Security • Financial Considerations • Qualifications of Personnel • Other Approval and Registrations	
7.2	HYPOTHESIS: Describe the hypothesis or what the study hopes to prove (Help Text updated 9/13)	:
In v	women with infertility requiring IVF or same-sex couples requiring IVF, we will see similar	

ı

7.3 AIMS: List the specific aims:

PRIMARY AIM:

To determine the outcomes of IVC with INVOcell device versus conventional IVF while using oral stimulation or minimal gonadotropins stimulation protocols on:

a. Implantation rate

SECONDARY AIMS:

To determine the outcome of IVC with INVOcell device versus conventional IVF while using oral stimulation or minimal gonadotropins stimulation protocols on:

- a. Fertilization rate
- b. Embryo quality
- c. Clinical pregnancy rate
- d. Live birth rate
- 7.4 DESIGN: Briefly describe the study design (e.g., observational, interventional, randomized, placebocontrolled, blinded, cross-over, cross-sectional, longitudinal, pharmacokinetic, etc.):

Non-blinded prospective randomized controlled trial pilot study

7.5 BACKGROUND AND SIGNIFICANCE: Briefly provide the background and significance of this study (e.g. why is this study needed) (space limit: one half page):

If this is a first in humans study, please summarize the safety data from the animal studies. For pediatric drug or device studies, please identify if this is the first study in pediatric populations.

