We expect N=20 to each group (cases and controls, respectively) and given low-stimulation protocols, expect 1-3 embryos per patient. Given these low numbers, summary statistics will be used. For categorical outcomes, frequency tables will be provided. For continuous outcomes, full summary statistics will be provided. This will include mean, standard deviation, minimum, maximum, median and quartiles. To determine the effect of IVC with INVOcell device versus conventional IVF while using oral stimulation or minimal gonadotropins stimulation protocols on: a. Fertilization rate, which is defined by the total number of fertilized oocytes divided by total number of mature oocytes retrieved. This comparison will take place on day-3, as that is when the IVC embryos will be assessed. b. Embryo quality. This is measured by the Gardner grading system. c. Implantation rate, which is defined by number gestational sacs seen on early pregnancy 6-week ultrasound divided by number of embryos transferred. d. Clinical pregnancy rate, which is defined by the number of fetal poles with heartbeat seen on ultrasound divided by the number of embryos transferred. e. Live birth rate, which is defined by the number of living babies delivered divided by the number of transfers. To determine the effect of IVC with INVOcell device versus conventional IVF while using oral stimulation or minimal gonadotropins stimulation protocols on: a. Live birth rate, which is defined by the number of live births divided by the number of transfers		ill be

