summary statistics will be provided. This will include mean, standard deviation, minimum, maximum, median and quartiles. To determine the effect of IVC with INVOcell device versus conventional IVF while using oral stimulation or minimal gonadotropins stimulation protocols on: a. Fertilization rate, which is defined by the total number of fertilized oocytes divided by total number of mature oocytes retrieved. This comparison will take place on day-3, as that is when the IVC embryos will be assessed. b. Embryo quality. This is measured by the Gardner grading system. c. Implantation rate, which is defined by number gestational sacs seen on early pregnancy 6-week ultrasound divided by number of embryos transferred d. Clinical pregnancy rate, which is defined by the number of fetal poles with heartbeat seen on ultrasound divided by the number of embryos transferred e. Live birth rate, which is defined by the number of living babies delivered divided by the number of transfers To determine the effect of IVC with INVOcell device versus conventional IVF while using oral stimulation or minimal gonadotropins stimulation protocols on: a. Live birth rate, which is defined by the number of live births divided by the number of transfers	We expect N=20 to each group (cases and controls, respectively) and given low-stimulation protocols, expect 1-3 embryos per patient. Given these low numbers, summary statistics will be	
a. Fertilization rate, which is defined by the total number of fertilized oocytes divided by total number of mature oocytes retrieved. This comparison will take place on day-3, as that is when the IVC embryos will be assessed. b. Embryo quality. This is measured by the Gardner grading system. c. Implantation rate, which is defined by number gestational sacs seen on early pregnancy 6-week ultrasound divided by number of embryos transferred d. Clinical pregnancy rate, which is defined by the number of fetal poles with heartbeat seen on ultrasound divided by the number of embryos transferred e. Live birth rate, which is defined by the number of living babies delivered divided by the number of transfers To determine the effect of IVC with INVOcell device versus conventional IVF while using oral stimulation or minimal gonadotropins stimulation protocols on: a. Live birth rate, which is defined by the number of live births divided by the number of transfers	summary statistics will be provided. This will include mean, standard deviation, minimum,	

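### The hypothesis names clinical pregnancy rate and the primary aim is implantation rate; as defined in 7.25, neither gives the proportion of randomised women who become pregnant

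*Combined protocol and SAP*

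**What the plan says.** - **Hypothesis (4.1).** The stated expectation is that "we will see similar clinical pregnancy rates (CPR") in the device arm and the conventional IVF arm.
- **Primary aim (4.1, repeated in 7.3).** One item only: "a. Implantation rate".
- **Secondary aims (4.1, 7.3).** The third item is "c. Clinical pregnancy rate".
- **Definitions (7.25).** "Implantation rate, which is defined by number gestational sacs seen on early pregnancy 6-week ultrasound divided by number of embryos transferred". "Clinical pregnancy rate, which is defined by the number of fetal poles with heartbeat seen on ultrasound divided by the number of embryos transferred". Live birth rate, by contrast, is divided by the number of transfers.
- **Analysis (7.25).** Summary statistics only, with no test and no margin for calling the arms similar.
- **Unit and time of randomisation (7.9, 7.13).** Patients are randomised, on the day of trigger.

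The hypothesis is stated again in 7.2, but the text available there breaks off after "same-sex couples requiring IVF, we will see similar". That is a gap in the extracted text. It is not counted against the plan, and nothing below relies on it.

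**The concern.** A plan normally lets its primary endpoint speak to its hypothesis. Here the hypothesis is about one quantity and the primary aim about another, and no readable text says why implantation was chosen or that it stands in for pregnancy.

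The definitions add a second difficulty. The hypothesis is about women with infertility, and women are randomised, but 7.25 expresses both rates per embryo transferred. The number of embryos transferred is fixed only after randomisation and after fertilisation and culture, the steps that differ between the arms. Section 12.2 says that the risk of failed embryo development may be slightly higher with the device. The denominator could therefore differ by arm because of the treatment. At stake is whether the pilot reports the comparison its hypothesis is about, and whether a larger trial planned from it would start from a clear endpoint.

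**Working it through.** The plan derives no figure from either endpoint, since 9.3 gives a pilot target without a calculation. There is nothing to reproduce. The check compares the definitions and then works through illustrative counts.

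**1. Definitions side by side (7.25)**

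| | Numerator | Denominator |
|---|---|---|
| Implantation rate (primary) | Gestational sacs, 6-week ultrasound | Embryos transferred |
| Clinical pregnancy rate (hypothesis; secondary) | Fetal poles with heartbeat | Embryos transferred |
| Not defined in the plan | Women with at least one heartbeat | Women randomised |

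The first two rows separate only when a sac shows no heartbeat. The documents give no rate for that, so the gap between them cannot be sized.

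**2. Equal pregnancy per woman, unequal reported rates**

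Inputs: 16 women per arm (9.1, 9.3). Assumed: 8 singleton pregnancies in each arm, every sac with a heartbeat, and 1.5 v 2.0 embryos transferred per woman. Section 7.25 expects 1-3 embryos per patient but does not say how many are transferred.

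- Per woman: 8/16 = 50% in both arms.
- Implantation rate: 8/(16 × 1.5) = 8/24 = 33% v 8/(16 × 2.0) = 8/32 = 25%.
- Clinical pregnancy rate as defined: 8/24 = 33% v 8/32 = 25%, the same two figures.
- With 1.0 v 2.0 embryos per woman (a wider assumed gap): 8/16 = 50% v 8/32 = 25% on both definitions.

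Section 7.25 gives 20 per group instead of 16. With half of 20 pregnant, the first case is 10/30 = 33% v 10/40 = 25%, so the choice of size does not matter here.

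**3. Equal reported rates, unequal pregnancy per woman**

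Assumed: 16 transfers, 32 embryos and 10 sacs per arm, every sac with a heartbeat.

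- Both rates as defined: 10/32 = 31.3% in each arm.
- Ten singletons in one arm: 10/16 = 62.5% of women pregnant.
- Five twin pregnancies in the other: 5/16 = 31.3% of women pregnant.

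**4. Women without a transfer**

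Such a woman adds nothing to the numerator or denominator of either rate, so she disappears from both. In a rate over all randomised women she counts as not pregnant.

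**5. The plan's own background (7.6)**

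In the cited randomised trial of this device, implantation per blastocyst favoured intravaginal culture by 54.5 − 44.4 = 10.1 points and birth per blastocyst by 48.5 − 41.7 = 6.8 points. The live birth rate favoured conventional IVF by 60 − 55 = 5 points. This is live birth, and 7.6 does not state the denominator of the last rate. It is supporting evidence only that per-embryo and other rates can point in different directions.

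**The case against.** The strongest reply is that little hangs on the label. The analysis is descriptive, no test or success rule attaches to the primary endpoint, and clinical pregnancy rate is a named secondary aim that will be summarised in both arms. Exchanging the labels would change no analysis, sample size or error rate. An embryo-level primary is also a legitimate choice for a small pilot of a culture device. All of this stands. It limits the point to interpretation and leaves the choice of primary with the sponsor.

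A second reply is that the arms share stimulation, retrieval and transfer (7.9), so a large difference in embryos transferred is not to be expected. This stands in part. The 1.5 v 2.0 and 1.0 v 2.0 inputs are assumptions, and nothing in the documents supports a twofold gap. But culture differs by arm, so the number of transferable embryos can differ too, and step 3 needs no difference in embryo numbers.

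Three stronger readings are tempting, and the documents do not support them:

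- A reader might infer that the hypothesis is already about a per-woman rate, so that the primary endpoint could differ by 8 to 25 points while the hypothesis held exactly. Section 7.25 divides clinical pregnancy by embryos transferred, so in step 2 both rates move together. The 8- to 25-point difference is between arms on both defined rates, set against equality per woman.
- A reader might infer that the pilot could not be judged against its hypothesis at all. Clinical pregnancy is reported as a secondary outcome. What prevents a firm statement of similarity is the small sample and the absence of a margin, and aligning the endpoints cures neither.
- A reader might infer that the plan presents its primary result as evidence on pregnancy rates. No readable text does so.

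**Conclusion.** The point holds in a limited form. The hypothesis in 4.1 and the primary aim in 4.1 and 7.3 name different endpoints, and nothing readable reconciles them. By the plan's own definitions those endpoints differ only in numerator, and neither measures the proportion of randomised women who become pregnant.

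The possible size is illustrative. Equal pregnancy per woman (50% v 50%) can appear as 33% v 25% on both defined rates, and equal defined rates (31.3%) can cover 62.5% v 31.3% of women pregnant. These figures rest on assumed embryo numbers, assumed twinning and a heartbeat in every sac. The consequence is unclear interpretation of a descriptive pilot. The point is worth correcting because the correction is one of wording and definition.

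**What to change.** 1. In 7.25, define clinical pregnancy as yes/no per randomised woman, meaning at least one fetal heartbeat on ultrasound. Report it by arm with all randomised women in the denominator, including those with no transfer. State which ultrasound counts, since 7.25 dates only the one used for implantation, and how a woman lost to follow-up is counted.
2. In 4.1 and 7.3, and in 7.2 if its full text needs it, use one endpoint for the hypothesis and the primary aim. Either make the per-woman clinical pregnancy rate primary with implantation rate secondary, or keep implantation rate primary, restate the hypothesis in terms of implantation, and report per-woman clinical pregnancy as secondary. The choice is the sponsor's.

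**Cost.** Wording in these sections and no new data. A per-woman rate has fewer units. Take the pregnancy rates of the cited non-randomised study in 7.6 (54.2% v 58.1%) as per-woman rates, which is an assumption. The half-width of a 95% interval at 16 per arm is then 1.96 × √(0.542 × 0.458/16 + 0.581 × 0.419/16) = 34 points. For that study's implantation rates (31.7% v 33.6%) at two embryos each it is 1.96 × √(0.317 × 0.683/32 + 0.336 × 0.664/32) = 23 points. Part of that apparent gain comes from treating embryos in the same woman as independent.

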7.1	This new consolidated section requests information about: • Hypothesis • Aims • Study Design • Background and Significance • Preliminary Studies • Procedures • Statistical Methods • References Later sections include: • Drugs and Devices • Sample Size, Eligibility, and Subjects • Recruitment and Consent • Risks and Benefits • Data and Safety Monitoring Plan • Confidentiality, Privacy and Security • Financial Considerations • Qualifications of Personnel • Other Approval and Registrations	
7.2	HYPOTHESIS: Describe the hypothesis or what the study hopes to prove (Help Text updated 9/13)	:
In v	women with infertility requiring IVF or same-sex couples requiring IVF, we will see similar	

ı

7.3 AIMS: List the specific aims:

PRIMARY AIM:

To determine the outcomes of IVC with INVOcell device versus conventional IVF while using oral stimulation or minimal gonadotropins stimulation protocols on:

a. Implantation rate

SECONDARY AIMS:

To determine the outcome of IVC with INVOcell device versus conventional IVF while using oral stimulation or minimal gonadotropins stimulation protocols on:

- a. Fertilization rate
- b. Embryo quality
- c. Clinical pregnancy rate
- d. Live birth rate
- 7.4 DESIGN: Briefly describe the study design (e.g., observational, interventional, randomized, placebocontrolled, blinded, cross-over, cross-sectional, longitudinal, pharmacokinetic, etc.):

Non-blinded prospective randomized controlled trial pilot study

7.5 BACKGROUND AND SIGNIFICANCE: Briefly provide the background and significance of this study (e.g. why is this study needed) (space limit: one half page):

If this is a first in humans study, please summarize the safety data from the animal studies. For pediatric drug or device studies, please identify if this is the first study in pediatric populations.

The focus of global reproductive health initiatives has traditionally placed an emphasis on improving maternal/child health (maternal mortality, neonatal mortality) as well as broadening the reach of contraception. Along these lines of fertility and family planning, we often forget that "family planning" includes the concept of fertility as well as *infertility*. Although there has been a reduction in child-seeking behavior amongst couples over time (meaning a decreased proportion), the prevalence of infertility has not changed very much from 1990-2010. In 2010, a World Health Organization (WHO) study found an estimated 48.5 million couples were infertile [1]. For women aged 20-44 attempting to conceive, 1.9% experienced primary infertility and 10.5% experienced secondary infertility [1]. Also, given the limitations with conducting population-based surveys in resource-limited settings and developing nations, these numbers may be drastically underestimated.

There is a great deal of stress and anxiety couples facing infertility experience. In developing nations and resource-limited settings, there is a significant level of stigma women suffering from infertility may also experience including: being ostracized from the community, verbal abuse and even physical abuse sometimes resulting in permanent injury or death [2]. The burden extends further, as those in remote areas have limited access to care in addition to the extensive costs required for workup and treatment [3]. For this reason, there is a need for cost-effective treatments that can be available for these women that do not rely on high-level technologies and 24-hour electricity availability [4]. Treatment can be as simple as ovulation induction with oral medications to as complicated and expensive as in-vitro fertilization (IVF) with the use of additional technologies (ie preimplantation genetic diagnosis).

For those patients requiring IVF treatment for management of their infertility, intra-vaginal culture (IVC) of embryos as a lower-cost alternative, which was first introduced in the 1980s, can be considered[4]. This can be performed using the INVOcell® device. There is a reduction in the cost of the treatment due to the following: 1) only one technician needed, 2) entire procedure including oocyte retrieval to placement of device can be completed in 60-90 minutes, 3) can be performed in a doctor's office/clinic setting and does not require lab or operating room, 4) does not rely on constant electricity to maintain laboratory and can be performed in load-shedding areas with unreliable electricity. There is also a psychological benefit as the woman can participate in the fertilization of the embryos first-hand in a more "natural" environment, as opposed to fertilization in a lab. In addition, this eliminates any chance of and reduces anxiety around embryo mix-ups [4].

7.6 PRELIMINARY STUDIES: Briefly summarize any preliminary studies relevant to your pro research (space limit: one half page):	posed
IVC, also called INVO, was developed by Claude Ranoux in 1988 as another method for culturing oocytes or embryos when compared to the conventional laboratory culture method [5]. Since then, the device has been used and studied in multiple countries including: Austria, Bolivia, Brazil, Canada, Ecuador, India, Mexico, Nicaragua, Pakistan, Panama, Spain, Turkey, and Venezuela [5-8]. In addition, INVOcell was FDA approved for use in the United States in November of 2015. There have been numerous studies on the INVO procedure and INVOcell device including evaluation and optimal conditions of the culture such as pH, pCO2 and pO2 [8] to optimal time of intra-vaginal culture [9]. Garcia-Ferreyra et al performed a prospective, non-randomized study that evaluated INVO using intracytoplasmic sperm injection (ICSI) with INVOcell versus conventional ICSI to day 3 and found no significant differences between embryo quality (77% INVO-ICSI versus 86.8% ICSI), pregnancy rate (54.2% INVO-ICSI versus 58.1% ICSI) and implantation rate (31.7% INVO-ICSI versus 33.6% ICSI) [10]. To control for factors between patients, a pilot study performed in 2015, compared sister ocytes (INVO vs IVF) and found similar cleavage rates (93% ± 1.5% IVF versus 97% ± 6% INVO) and a clinical pregnancy rate of 43% per embryo transferred from INVO procedure. In the United States, the device has been FDA approved for IVC for three days, but there is currently research being done to investigate whether IVC for five days (to blastocyst stage) can lead to improved embryo quality and live birth rates. Doody et al performed a randomized controlled trial comparing IVF to IVC that showed no significant differences in the percentage quality of blastocyst transferred when compared to IVF (87.9% IVC, 97.2%, p = 0.09) and live birth rate (55 % IVC, 60 % IVF) [9]. In fact, the implantation and birth rates per blastocyst transferred was actually higher with INVOcell wersus IVF (54.5 versus 44.4% and 48.5 versus 41.7%) [9]. These findings are promising and show that	
7.7 * TREATMENT PROTOCOL: Is this a treatment study, i.e. does this study intend to provid to individuals with a medical or psychological condition: (REQUIRED)	e treatment
⊙ Yes ○ No	
7.8 * COMMON RESEARCH ACTIVITIES: Types of research activities that will be carried out. apply and describe in more detail in the 'Procedures / Methods' section: (REQUIRED)	Check all that
 □ Interviews, questionnaires, surveys □ Educational or cognitive tests □ Focus groups ☑ Observation ☑ Non-invasive imaging or testing (MRI, EEG, pulse oximetry, etc.) □ Administration of contrast agent □ Imaging procedures or treatment procedures that involve radiation (x-rays, CT scans, CT-guided biopsies, DEXA scans, MUGA or PET scan) □ Biopsy conducted solely for research purposes □ Use of placebo □ Sham surgical procedure □ Collection of data from wearable tech such as Fitbit, Apple Watch, Garmin, motion actigraphs, etc.) 	

☐ Fitness tests or other exertion activities ☐ Use of mobile health apps or other apps

☐ Social media-based research activities☐ None of the above	
7.9 * PROCEDURES / METHODS: (REQUIRED)	
For clinical research, list all study procedures, tests and treatments required for this study, including when and how often they will be performed. If there are no clinical procedures, describe the research activities.	
If some of the activities would occur even if the person were not in the study, as in the case of treatment or tests performed for diagnostic purposes, clearly differentiate between those activities that will be done solely for research purposes and those that are happening as part of routine care.	
Examples may include:	
 additional scans outside standard clinical diagnosis or monitoring additional biopsies to collect tissue for research extra clinic visits extra lab tests not required for clinical care 	
If you have a procedure table, attach it to the submission with your other study documents.	
Patients will be randomized to intra-vaginal culture (IVC) of embryos using INVOcell or traditional in-vitro fertilization (IVF) of embryos. Both groups of patients will receive the same initial workup, consultation and evaluation, ovarian stimulation, cycle monitoring, oocyte retrieval, and embryo transfer. The only difference between the two groups will be the culturing/growth of the embryos, which will be randomized to IVC or IVF. All embryos will be transferred on day 3. The IVC protocol is attached for reference.	
7.10 STANDARD CLINICAL PRACTICE: To what extent, if any, do the planned research proc from the care that people would otherwise receive at this institution or the study site done locally:	
The only difference in clinical practice the "cases" from this randomized controlled trial would have that differed from the "control" population, would be the use of intravaginal culture (IVC) using the INVOcell device instead of the standard in-vitro fertilization (IVF) for fertilization and growth of embryos.	
7.12 * BIOSPECIMEN COLLECTION: Are you drawing any blood or collecting other biosamp buccal swabs, urine, saliva, hair, etc.): (REQUIRED)	les (e.g. tissue,
● Yes ○ No	
* Could this study generate genetic data that may be broadly shared (e.g., submitted to NIH in compliance with Genomic Data Sharing (GDS)/Genome-Wide Association Studies (GWAS) requirements): (REQUIRED)	
○ Yes • No	

Based on current research trends, we strongly recommend including the genomic data sharing language in the consent form to allow future sharing, even if you don't anticipate it now. It's easier than trying to reconsent all the specimen donors! 7.13 * TYPE OF SPECIMENS (check all that apply): (REQUIRED) **▼** Blood Tissue (describe below): Existing/archival materials (name source below): --Other (describe below): Describe and/or name source: Because patients will not be randomized to either arm of the study (IVC versus IVF) until the day of trigger, they will receive the standard of care and workup that all infertility patients receive when they come to UCSF Center for Reproductive Health for their care. No additional blood tests, tissue collection or biopsies will be performed beyond the standard of care. Therefore, all patients will have their blood drawn for evaluation of the etiology of their infertility, possible tracking hormone levels during their stimulation cycle, and have embryo transfers performed. 7.14 * SPECIMENS ARE: (check all that apply): (REQUIRED) Leftover specimens from a clinical diagnostic or therapeutic procedure Specimens collected for research purposes only (including extra samples taken during a clinical procedure) ✓ Other Explain **Other**: Specimens collected will be the same that are all part of standard care for patients under infertility evaluation. These include: blood samples and embryos (that will belong to patient and be transferred to uterus or frozen for later use by patient). 7.15 * DESTINATION: Specimens will ultimately be stored (check all that apply): (REQUIRED) Outside Entity: Cooperative group bank □ NIH ☐ Other university Industry sponsor Other UCSF: UCSF repository/bank being established under this protocol Existing UCSF specimen repository/bank with CHR approval Other location at UCSF (please describe) Provide the name of the bank and iRIS approval number (if not being

University of California San Francisco - Center for Reproductive Health - Embryology Lab

the location or lab:

banked at UCSF under this protocol). If you checked 'Other,' please provide

Embryology Lab - 6th floor Center for Reproductive Health [name] 7.18 * FUTURE SPECIMEN USE: Will any specimens or portions of specimens be retained after the study is over for possible use in future research studies: (REQUIRED) 7.20 * CLINICAL FOLLOW-UP DATA: Will clinical follow-up data be linked to specimens (i.e., will medical record information continue to be abstracted after the specimen is collected): (REQUIRED) 7.20 * CLINICAL FOLLOW-UP DATA: Will clinical follow-up data be linked to specimens (i.e., will medical record information continue to be abstracted after the specimen is collected): (REQUIRED) 7.20 * CLINICAL FOLLOW-UP DATA: Will clinical follow-up data be linked to specimens (i.e., will medical record information or follow-up or 'Indefinitely': Indefinitely, as patients may return for use of their embryos for next child. 7.25 STATISTICAL METHODS: Briefly summarize the methods and types of analyses that will be performed: This study will be a pilot study which will potentially lead to a larger randomized controlled trial. We expect N=20 to each group (cases and controls, respectively) and given low-stimulation protocols, expect 1-3 embryos per patient. Given these low numbers, summary statistics will be used. For categorical outcomes, frequency tables will be provided. For continuous outcomes, full summary statistics will be provided. This will include mean, standard deviation, minimum, maximum, median and quartiles. To determine the effect of IVC with INVOcell device versus conventional IVF while using oral stimulation or minimal gonadotropins stimulation protocols on: a. Fertilization rate, which is deffined by the total number of fertilized ocytes divided by total number of mature ocytes retrieved. This comparison will take place on day-3, as that is when the IVC embryos will be assessed. b. Embryo quality. This is measured by the following formation state, which is deffined by unumber gest total poles with heartbeat seen on ultrasound divided	7.16 UCSF-BANK PHYSICAL LOCATION: The repository/bank is physically located at (list the room number for all locations):	ne address and
Over for possible use in future research studies: (REQUIRED) C Yes © No 7.20 **CLINICAL FOLLOW-UP DATA: Will clinical follow-up data be linked to specimens (i.e., will medical record information continue to be abstracted after the specimen is collected): (REQUIRED) *Overline of the provide duration of follow-up or 'indefinitely': Indefinitely, as patients may return for use of their embryos for next child. 7.25 **STATISTICAL METHODS: Briefly summarize the methods and types of analyses that will be performed: This study will be a pilot study which will potentially lead to a larger randomized controlled trial. We expect N=20 to each group (cases and controls, respectively) and given low-stimulation protocols, expect 1-3 embryos per patient. Given these low numbers, summary statistics will be used. For categorical outcomes, frequency tables will be provided. For continuous outcomes, full summary statistics will be provided. This will include mean, standard deviation, minimum, maximum, median and quartiles. To determine the effect of IVC with INVOcell device versus conventional IVF while using oral stimulation or minimal gonadotropins stimulation protocols on: a. Fertilization rate, which is defined by the total number of fertilized oocytes divided by total number of mature oocytes retrieved. This comparison will take place on day-3, as that is when the IVC embryos will be assessed. b. Embryo quality. This is measured by the Gardner grading system. c. Implantation rate, which is defined by the Gardner grading system. c. Implantation rate, which is defined by the formation of fetal poles with heartbeat seen on ultrasound divided by mumber of embryos transferred d. Clinical pregnancy rate, which is defined by the number of fetal poles with heartbeat seen on ultrasound divided by the number of mumber of fetal poles with heartbeat seen on ultrasound divided by the number of mumber of provided by the number of inving babies delivered divided by the number of transfers To determine the effect of IVC with IN	Center for Reproductive Health [name]	
